6.5.2.3 Physical examination and vital signs

A complete physical examination and vital signs assessment will be performed at select study visits, as listed in the study schedule of events. A complete physical examination includes a review of the following systems: general appearance, head/eyes/ears/nose/throat (HEENT); neck; respiratory; cardiovascular; lymph nodes; abdomen; skin; musculoskeletal; and neurological. At all other scheduled visits, an abbreviated physical examination including exam of general appearance, skin, respiratory, cardiovascular, and abdomen will be conducted.

Vital signs including sitting blood pressure (systolic and diastolic), pulse rate, respiratory rate, and temperature will be collected after sitting for 3-5 minutes. Body weight will also be measured.

After Screening, any clinically significant abnormal findings in physical exams or clinically significant vital signs should be reported as AEs.

6.5.2.4 12-lead ECGs

Standard, digital, 12-lead ECGs will be performed at all time points as indicated in the Study Schedule of Events. Additional 12-lead ECGs should be performed at any other time if clinically indicated. The performance of all ECGs must adhere to the following guidelines:

- All standard digital ECGs will be performed after the patient has been supine for at least 5 minutes.
- The ECG will be performed before any other procedures that may affect heart rate (e.g., blood draws).
- The ECG will be performed prior to dosing.
- When ECG time points coincide with PK blood sampling time points, the ECG must be performed before blood sampling so that any patient's response to the blood sampling does not cause a change in ECG interval durations.

A hard copy of the ECG will be printed at the site. To ensure safety of the patients, the Investigator or designee at the Investigator site will make comparisons to baseline measurements, which is defined as the most recent non-missing (scheduled or unscheduled) measurement collected prior to the initial administration of study drug. If a clinically significant finding is noted at any time on ECG, site will follow-up with a cardiology consult to verify initial ECG findings and further evaluate safety of patient.

See Study Procedures or Study Schedule of Events (Table 1) for assessment days.

6.5.2.5 Immunogenicity (anti-SelK2 antibodies) assessment

Serum samples will be collected according to the procedure described below:

Blood sampling will be performed to supply at least 1 mL of serum for immunogenicity assessments in patients randomized to the SelK2 arm or adaptive arm. Blood samples will be collected via an indwelling catheter and/or via direct venipuncture.

The exact date and sampling time will be recorded on the appropriate eCRF page. Please refer to the Laboratory Manual for details of collection, storage, and shipping of samples.

Immunogenicity evaluations will be performed at Cytovance Biologics, [name].

6.5.2.6 Urine Pregnancy test

A urine pregnancy tests will be performed on all woman of child-bearing potential at the site on the Day 1 prior to randomization. If the urine pregnancy test is positive and confirmed as correct, patient will not be allowed to be randomized into this clinical study.

7.0 ADVERSE EVENTS INCLUDING SPECIAL REPORTING REQUIREMENTS FOR POTENTIAL VTE AND BLEEDING ENDPOINT EVENTS

7.1 Procedures for Handling and Reporting Adverse Events

7.1.1 Adverse Event

An **adverse event** (AE) is any undesirable medical event affecting a patient during a clinical trial. An AE can therefore be defined as any sign, symptom, syndrome, or new illness that appears while a patient is participating in this clinical study (from Randomization to final study visit (either Day 57 Visit or Early Discontinuation Visit)) or, if present at baseline, worsens in a patient during the period of observation in the clinical study and that may impair the well-being of the patient. The term also covers laboratory findings or results of other diagnostic procedures that are considered to be medically important (e.g., that require unscheduled diagnostic procedures, treatment measures, or result in withdrawal from the study). An AE may or may not have a causal relationship with the study drug. The period of observation for AEs is defined as from the point at which the patient is randomized into the study to the completion of the Follow-Up Phase assessments at Day 57 (or the Early Discontinuation Visit, if patient early discontinues).

An AE may be:

- A new illness;
- Worsening of a sign or symptom of the condition under treatment or of a concomitant illness;
- An effect of the study drug;
- Unrelated to participation in the clinical study; or
- A combination of one or more of these factors.

Surgical procedures themselves are not AEs; they are therapeutic measures for conditions that require surgery. However, the condition for which the surgery is required may be an AE. Planned surgical measures permitted by the study protocol and the condition(s) leading to these measures are not AEs.

Each AE is to be recorded only once on the “Adverse Event” eCRF page with *seriousness* and maximum *intensity* that occurred over the duration of the event. Each event also should be evaluated with respect to *causality* and *actions taken*. All AEs are to be monitored and recorded from the point of study Randomization through Day 57 (or earlier if patient discontinues from the study). For all AEs that require the patient to be discontinued from the study, the event(s) will be followed until final resolution or stabilization of the event(s). Note that unexpected SAEs should be reported as outlined in Section 7.1.2. Adverse events may be identified by spontaneous patient report or from standardized open-ended verbal probes.

The Investigator will classify and evaluate each AE as follows:

- Seriousness (see definition of SAEs in *Section 7.1.2*);
- Intensity (“Mild” [does not interfere with daily activities]; “Moderate” [interferes with daily activities]; “Severe” [prevents daily activities]);

- Relationship to study drug (Not Related [clearly not related to study drug], Unlikely Related [doubtfully related to the study drug], Possibly Related [may be related to study drug], Probably Related [likely related to study drug] or Definitely Related [clearly related to study drug]);
- Action taken (None, Required concomitant medication, Other [explain]); and
- Outcome (Recovered without sequelae, Resolved with sequelae, Ongoing, Unknown, Death).

Procedures Regarding Pregnancy

Pregnancy is considered an AE. Should a female patient become pregnant (must be confirmed by the serum pregnancy test) during the study, the medical monitor should be immediately notified, and the patient followed to term. Should the female partner of a male patient become pregnant during the male patient's enrollment in this study, the medical monitor should be immediately notified, and the male patient's partner should be followed to term, if consent is received by her.

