3.4.2 Treatment Phase

After assessment that the patient has met all Inclusion Criteria and none of the Exclusion Criteria, on the day PRIOR to the scheduled TKA surgery, the patient will be randomized into this study. Prior to dosing of any study drug, baseline safety assessments will be taken.

For those randomized to receive SelK2, patients will receive a single dose of 7.5 mg/kg SelK2 via IV administration at least 12 hours prior to but not longer than 24 hours prior to the start of the TKA surgery. The Treatment Phase of the study consists of the period from the dosing of study drug (SelK2 or enoxaparin) or the TKA (for enoxaparin arm, if enoxaparin dosing is only done after TKA) up to the day of venography (Day 11 \pm 2) or early study termination. Note that for patients randomized to receive SelK2, study drug can be dosed either the day prior to TKA (Day 1) or on the day of TKA (Day 2) as long as the dosing occurs at least 12 hours prior to but not longer than 24 hours prior to the start of the TKA surgery.

For those randomized to receive enoxaparin, patients will receive 40 mg enoxaparin administered via SC injection 12 hours after TKA surgery followed by daily SC injections of 40 mg enoxaparin for at least 9 additional days post-surgery (with the option of giving an additional 40 mg enoxaparin SC dose 12 hours prior to TKA surgery).

For those randomized to receive SelK2 and enoxaparin, patients will receive a single dose of 7.5 mg/kg SelK2 via IV administration at least 12 hours prior to but not longer than 24 hours prior to

the start of the TKA surgery and will receive 40 mg enoxaparin administered via SC injection 12 hours after TKA surgery followed by daily SC injections of 40 mg enoxaparin for at least 9 additional days post-surgery.

For all patients, the Treatment Phase will be completed on the day the venography is completed.

Patients will remain in the hospital for AT LEAST two overnights after TKA. During the Treatment Phase, efficacy, safety and PK/PD/Immunogenicity assessments will be completed for each patient.

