10.4.1 Adverse Events

For analyses purposes, adverse events will be classified as pre-treatment emergent, treatment emergent, or post-treatment emergent. Adverse events which start (or increase in severity) during the period from the signing of informed consent up to, but not including, the first dose of study drug will be considered pre-treatment emergent. Adverse events which start (or increase in severity) during the period from the first dose of study drug through completion of the final Follow-up Visit (Day 57) will be considered treatment emergent. Adverse events which start (or increase in severity) after the completion of the Follow-Up Visit will be considered post-treatment emergent. For AEs with partial start dates, missing month will be imputed with January and missing day will be imputed with 1.

Adverse event summary tables will be presented for AEs only and will include the following:

- All treatment-emergent adverse events (TEAEs) or by severity or by relationship,
- Related (defined as possibly related or related) TEAEs,
- TEAEs leading to treatment discontinuation,
- Serious TEAEs, and
- Frequently reported TEAEs.

Summaries will be presented by Medical Dictionary for Regulatory Activities (MedDRA) system organ class and preferred term using frequency counts and percentages (i.e., number and percentage of patients with an event as well as total number of events). Patients with multiple occurrences of the same adverse event or a continuing adverse event will be counted once; only the maximum severity level of this AE will be presented in the severity summaries; and only the worst/highest relationship level of this AE will be presented in the relationship summaries. A separate table will summarize all TEAEs when each of them is considered unique, hereafter referred as adverse event count table. In addition, a listing containing individual patient adverse event data for all deaths and other serious and significant adverse events will be provided, separately. All adverse events including pre- and post-treatment adverse events will be presented in individual patient data listings.

Narratives of deaths, serious and significant adverse events, including early withdrawals due to adverse events, will also be provided.

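### AEs are recorded once, at maximum intensity, so the worsening limb of the treatment-emergent rule cannot be derived for AEs starting between randomization and first dose, mainly affecting enoxaparin-only patients without a pre-operative dose

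*Combined protocol and SAP*

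**What the plan says.** Section 7.1.1 sets the recording rule: "Each AE is to be recorded only once on the" AE page, carrying seriousness and the maximum intensity "that occurred over the duration of the event". The investigator also rates relationship, action taken and outcome. Collection starts at randomization: "All AEs are to be monitored and recorded from the point of study Randomization through Day 57". A condition counts as an AE in its own right if, "if present at baseline, worsens in a patient during the period of observation".

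Section 10.4.1 sets the classification rule. The treatment-emergent class is "Adverse events which start (or increase in severity) during the period from the first dose of study drug through completion" of the Day 57 visit. An AE that starts or worsens in the period "up to, but not including, the first dose of study drug will be considered pre-treatment emergent". The list of AE summary tables opens with "All treatment-emergent adverse events (TEAEs) or by severity or by relationship", and the other entries are also restricted to treatment-emergent AEs. Pre-treatment AEs appear in individual patient listings.

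On dosing, Sections 5.2.1 and 5.2.3 place the SelK2 infusion 12 to 24 hours before surgery, alone or in combination. Section 5.2.2 places the first enoxaparin dose 12 hours after surgery, with an optional extra dose 12 hours before it. Section 3.4.2 allows for this difference when it defines the Treatment Phase, which begins at study drug dosing "or the TKA (for enoxaparin arm, if enoxaparin dosing is only done after TKA"). Section 10.4.1 has no matching provision.

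**The concern.** The classification rule needs information that the recording rule does not collect. To say that an AE became worse after first dose, the analyst needs its grade before the dose, or the date on which the grade rose. One record at peak intensity gives neither.

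This matters because the arms reach first dose at different points relative to surgery. An enoxaparin-only patient with no pre-operative dose goes through anaesthesia, the operation and the first 12 post-operative hours before first dose. A SelK2 patient has already been dosed. An AE that begins in those hours and then worsens is treatment emergent by onset in a SelK2 patient. In the enoxaparin patient it depends entirely on the worsening limb.

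Overall safety and tolerability is a primary objective (Section 2.0), and treatment-emergent AE incidence is a named safety endpoint (Section 10.4). An arm-dependent misclassification would affect the comparison in those tables. If onset date decided the class, it would undercount comparator AEs and make SelK2 look relatively worse.

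**Working it through.** The plan gives no figure on this point, so there is none to reproduce. The check sets the two rules side by side and then works out where they fail.

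**Step 1. What one AE record can show.** Section 7.1.1 provides maximum intensity, seriousness, relationship, action and outcome. It requests no grade at first dose, no date of severity change and no second record when an AE already entered gets worse.

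**Step 2. Apply Section 10.4.1 to each kind of AE.**

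| AE | Derivable? | Reason |
|---|---|---|
| Starts after first dose | Yes | Onset is enough |
| Condition present before randomization, worsens after first dose | Yes | The worsening is a new AE with its own start |
| Starts between randomization and first dose, never worsens | Pre-treatment by onset | But the record cannot confirm that it never worsened |
| Starts between randomization and first dose, worsens after the dose | No | The peak grade is known; its timing is not |

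The last AE meets both definitions in Section 10.4.1: pre-treatment by its start and treatment emergent by its worsening. No precedence rule or fallback is given.

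**Step 3. Length of the pre-dose period by arm.** From the plan: first enoxaparin dose 12 h after surgery. Assumed: surgery lasts 1 to 3 h, and randomization is 12 to 24 h before surgery.

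- Enoxaparin only, no pre-operative dose, from start of surgery: 1 + 12 = 13 h to 3 + 12 = 15 h.
- The same patients, from randomization: 12 + 1 + 12 = 25 h to 24 + 3 + 12 = 39 h.
- Enoxaparin with the pre-operative dose, and both SelK2-containing arms: first dose precedes surgery. Every AE starting during or after surgery is treatment emergent by onset, and the worsening limb is needed only for the interval between randomization and that dose.

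**Step 4. Number affected.** Let N be the arm size, p the share given the pre-operative dose, a the share of the others with an AE starting between surgery and first dose, and w the share of those whose AE then worsens. The expected number of patients is N × (1 − p) × a × w. Only N = 95 is in the plan. The pre-operative dose is at the investigator's discretion, so p can be anything from 0 to 1, and a and w are not given. At p = 1 the result is zero whatever a and w are. No count can be derived.

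**Step 5. Can programming repair it?** Using onset date alone removes AEs that did worsen on enoxaparin. Counting every undatable case as treatment emergent keeps them, but also admits AEs that never worsened or that peaked before the dose. Neither reproduces the rule in Section 10.4.1. The information has to be collected at the time.

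**The case against.** **Worsening is already an AE.** Section 7.1.1 makes worsening of a baseline condition an AE, so a reader who infers that the worsening limb fails altogether goes too far. That part of the objection stands for conditions present before randomization. It does not clearly cover an AE that arises during surgery: the period of observation starts at randomization, so the event is already on the AE page and the one-record rule applies. The ECG section (6.5.2.4) defines baseline as the last value before first study drug, but nothing extends that definition to AEs.

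**The eCRF guidelines may settle it.** Section 6.5.2.1 refers to a separate document on AE completion, which is not available here. It could contain a rule for splitting records. To solve the problem it would have to depart from Section 7.1.1, so the protocol text still needs to change.

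**Lost AEs are an inference.** A reader might conclude that peri-operative AEs which worsen on enoxaparin are certain to drop out of that arm's tables. The plan does not say so. It happens only if classification falls back on onset date, and no fallback is stated.

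**A patient count is tempting.** Suppose 30% of the arm had an AE starting between surgery and first dose and 10% to 30% of these worsened. With no pre-operative dosing, 0.30 × 0.10 = 3% to 0.30 × 0.30 = 9% of 95 gives about 3 to 9 patients. Both rates are assumptions with no source in the documents. At 50% pre-operative dosing the figure halves, and a patient with another treatment-emergent AE still counts in the overall incidence.

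**Key safety results are untouched.** This stands. The primary safety outcome is major or clinically relevant non-major bleeding during the Treatment Phase, which starts at surgery for these patients. Section 10.4 tabulates adjudicated bleeding with no treatment-emergent restriction, and serious and pre-treatment AEs are listed.

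**The window start is the larger issue.** This also stands. Most of the between-arm difference comes from counting AEs from first dose, whether or not they worsen.

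**Conclusion.** The point holds in a limited form and is minor. As written, Sections 7.1.1 and 10.4.1 cannot both be followed for an AE that starts between randomization and first dose and worsens later. In practice the gap concerns enoxaparin-only patients without the pre-operative dose, over an interval of about 13 to 15 hours from the start of surgery if surgery lasts 1 to 3 hours.

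What is exposed is the descriptive treatment-emergent summaries, including those by severity and relationship. The direction of error depends on an unstated fallback: under onset date, enoxaparin AEs are undercounted. The number of patients is unknown and could be zero. The conclusion assumes that the unseen eCRF guidelines follow Section 7.1.1.

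**What to change.** In Section 7.1.1 and the eCRF completion guidelines, require a new AE record, with start date and time and the new intensity, whenever an AE that began before first dose worsens after it. Time of day is needed because surgery and the first post-operative enoxaparin dose are both scheduled for Day 2. State in Section 10.4.1 that the worsening limb is derived from these records. Keep one record at maximum intensity for all other AEs.

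The cost is one protocol sentence, a guideline update and a few extra AE entries.

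This does not remove the separate imbalance from AEs that start between surgery and first enoxaparin dose and never worsen: they are pre-treatment in these patients and treatment emergent in SelK2 patients. For that, tabulate AEs in all arms from a common start, either randomization, as Section 10.4 already has for the safety analysis, or the TKA.

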7.1.2 Serious Adverse Event

A **serious adverse event (SAE)** is any AE that, at any dose of study drug or at any time during the period of observation:

- Results in death;
- Is immediately life-threatening;
- Requires or prolongs in-patient hospitalization;
- Results in persistent or significant disability/incapacity or substantial disruption of the ability to conduct normal life functions;
- Involves congenital anomaly or malignancy;
- Is medically important; or
- Requires medical intervention to prevent permanent impairment or damage.

Hospital admissions and/or surgical operations planned before or during a study are not considered AEs/SAEs if the illness or disease existed before the patient was enrolled in the study, provided that it did not deteriorate in an unexpected way during the study.

“Medically important events” are events that may not be immediately life threatening or result in death or hospitalization, but may jeopardize the patient or require intervention to prevent one of the other outcomes listed in the definition above. Examples of such events are intensive treatment in an emergency room or at home for allergic bronchospasm, blood dyscrasias or convulsions that do not result in hospitalization, or the development of drug dependency or drug abuse. Such events should be documented and reported as SAEs via data entry into the appropriate eCRF (see Reporting Requirements below).

“Events requiring medical intervention to prevent permanent impairment or damage” are events where the Investigator believes that medical or surgical intervention is necessary to preclude permanent impairment of a body function or to prevent permanent damage to a body structure. As there is an overlap between the terms “medically important event” and “events requiring medical

intervention to prevent permanent impairment or damage", it is left to the discretion of the Investigator to select the more applicable of the two criteria when entering data on the eCRF about the SAE.

Reporting Requirements for Serious Adverse Events Are As Follows:

All serious adverse events (SAEs) that occur from the time of randomization through the end of the study (Day 57 Visit), whether or not considered related to study drug, must be reported via data entry into the appropriate eCRF or fax within 24 hours of occurrence.

Sites will be provided with phone and faxline numbers for each country, on the paper SAE back up form.

All SAEs should be reported immediately to the sponsor except for those SAEs that the protocol or other document (e.g., Investigator's Brochure) identifies as not needing immediate reporting. The immediate reports should be followed promptly by detailed, written reports. The immediate and follow-up reports should identify subjects by unique code numbers assigned to the trial subjects rather than by the subjects' names, personal identification numbers, and/or addresses. The investigator should also comply with the applicable regulatory requirement(s) related to the reporting of unexpected serious adverse drug reactions to the regulatory authority(ies) and the IRB/IEC.

The Sponsor or its designated Contract Research Organization (CRO) will ensure that all regulatory reporting requirements are met.

7.1.3 Safety Reporting to Health Authorities, Independent Ethics Committees/ Institutional Review Boards

The sponsor will send appropriate safety notifications to Health Authorities in accordance with applicable laws and regulations. The investigator must comply with any applicable site-specific requirements related to the reporting of SAEs (and in particular deaths) involving his/her subjects to the IEC/IRB that approved the trial. In accordance with ICH GCP guidelines, the sponsor will inform the investigator of "findings that could adversely affect the safety of subjects, impact the conduct of the trial, or alter the IEC's/IRB's approval/favorable opinion to continue the trial." In particular and in line with respective regulations, the sponsor will inform the investigator of AEs that are both serious and unexpected and are considered to be related to the administered product ("suspected unexpected serious adverse reactions" [SUSARs]). The investigator should place copies of Safety reports in the Investigator Site File. National regulations with regard to Safety report notifications to investigators will be taken into account. When specifically required by regulations and guidelines, the sponsor will provide appropriate Safety reports directly to the concerned lead IEC/IRB and will maintain records of these notifications. When direct reporting by the sponsor is not clearly defined by national or site-specific regulations, the investigator will be responsible for promptly notifying the concerned IEC/IRB of any Safety reports provided by the sponsor and of filing copies of all related correspondence in the Investigator Site File. For trials covered by the European Directive 2001/20/EC, the sponsor's responsibilities regarding the reporting of SAEs/SUSARs/Safety Issues will be carried out in accordance with that Directive and with the related Detailed Guidances.

